For all medications (including fluids, anti-emetics, analgesics) associated with management of acute angioedema attacks, study personnel will record start/stop dates, time of administration, dose, unit, frequency, and route of administration in the subject's CRF page. Adverse events associated with medications used in the treatment of acute angioedema attacks will be captured on the AE CRF and attributed to the concomitant medication administered (Section 8.1.2).

Adult subjects receiving long-term prophylaxis with C1 INH prior to randomization may be randomized to treatment sequences that contain a placebo treatment period (ie, A/B or B/A); such subjects remain eligible for on-demand therapy as outlined above. If, after receipt of at least 3 weeks of investigational product, the subject's quality of life significantly deteriorates and interferes with daily living routines, and the subject experiences a 2-fold increase in attack frequency with greater severity (relative to the subject's baseline without prophylaxis), following discussion of the investigator with the sponsor, subject may be discontinued from the treatment.

The investigator will be responsible for entering information about the subject's discontinuation from study drug in the CRF and where applicable, perform study related procedures as outlined in Table 3. The investigator will also ensure the subject receives appropriate treatment based on the subjects past HAE treatment and according to local standard of care. Angioedema attacks will not be considered AEs; however, events satisfying the serious criteria should be recorded as a SAE and reported to Shire Pharmacovigilance (Section 8.1.4). Data on angioedema attacks will be collected separately from general reports of AEs and will be used in the evaluation of efficacy (Section 7.2.2). In addition, if applicable, subjects will record their response to icatibant therapy when used for treating an angioedema attack, as well as any associated side effects or tolerability issues. This information will be recorded in the electronic subject diary (Section 7.2.2.4).

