7.2.3.10 Injection Site Reactions

Investigational product SC injection site reactions will be captured in the local tolerability CRF. Site personnel will distinguish between injection site reactions related to the procedure (eg, will check for redness after needle is inserted and prior to investigational product administration) vs the actual investigational product. Injection site reactions that do not meet the criteria of an SAE will not need to be reported as an AE.

Subcutaneous injection site reactions will be assessed at the following post-injection time points in each treatment period: 15 minutes, 30 minutes, and 1 hour post-injection. Study personnel will examine injection sites for erythema or swelling and will question the subject to collect information on cutaneous pain, burning sensation, itching/pruritus, and warm sensation. The diameter of any erythema or swelling should be measured to obtain the severity grading. The injection site reactions will be graded as absent, mild, moderate, or severe using the scoring criteria shown in [Table 8](#). Both the severity score and the measurement of any erythema or swelling are to be captured in the CRF. In addition, the overall impact of injection site reactions on daily living (yes/no) and duration will be assessed at the last visit of each treatment period (Visits 28a and 28b).

Table 8 Severity Scoring for Injection Site Reactions

Reaction	Severity		
	Mild	Moderate	Severe
Erythema	>0 to 5 cm	>5 to 10 cm	>10 cm
Swelling	>0 to 5 cm	>5 to 10 cm	>10 cm
Cutaneous pain	Mild discomfort to touch	Discomfort with movement	Significant discomfort at rest
Burning sensation	Mild burning sensation, which is easily tolerated	Moderate burning sensation, causing some discomfort	Severe burning sensation, causing significant discomfort
Itching/pruritus	Mild itching/pruritus, which is easily tolerated	Moderate itching/pruritus, causing some discomfort	Severe itching/pruritus, causing significant discomfort
Warm sensation	Mild warmth to touch	Moderate warmth to touch	Significant warmth to touch

Injection site reactions resulting from the administration of icatibant (as rescue medication for acute angioedema attacks) will be reported as an AE with causality linked to icatibant.

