11.1 Adverse Events

Adverse events will be coded using the Medical Dictionary for Regulatory Activities (MedDRA), Version 19.0 adverse events dictionary.

Adverse events will be collected from the time of informed consent through 7 days after the last dose date of investigational product. All serious adverse events (SAE) that occur \leq 30 days after the last dose date of investigational product and related SAEs that occur >30 days after the last dose date of investigational product will be collected.

An adverse event that increases in severity will be captured as a new event. An AE that develops into a SAE will be captured as a new event from the date it met the seriousness criteria. Worsening of pre-treatment events, after initiation of investigational product, will be recorded as new AE. An AE (classified by preferred term) that occurs during the study will be considered a treatment emergent adverse event (TEAE) if the start date and time of the AE is on or after the first dose date of investigational product and up to 7 days after the last dose of investigational product and up to 30 days after the last dose of investigational product, or with an increase in severity on or after the date and time of the first dose.

In addition, angioedema attacks and ISRs will not be considered AEs unless they satisfy serious criteria according to the protocol.

The number and percentage of subjects reporting any TEAEs, SAEs, and TEAEs related to investigational product, TEAEs leading to withdrawal, Severe TEAEs and absolute count of events will be summarized. Angioedema attacks and ISRs will not be considered AEs unless they satisfy serious criteria according to the protocol.

The number and percentage of subjects reporting any TEAEs, and absolute count of events will also be summarized in the following ways:

- By SOC, preferred term and treatment
- By SOC, preferred term, treatment and maximum severity
- By SOC, preferred term, treatment and relationship to investigational product in the opinion of the investigator
- By preferred term

TEAEs leading to withdrawal, SAEs, and deaths will be similarly summarized as TEAEs.

CONFIDENTIAL

Shire SHP616-300 Statistical Analysis Plan idursulfase IT

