11.5 Injection Site Reaction

A summary of SC injection site reactions will be summarized by treatment. The categories in this summary include: any injection site reaction, any severe reaction, any mild reaction, and any moderate reaction. Subjects will be counted in each category only once, the worst reaction among 15 assessments will be counted. The percentage will be calculated from the total number of subjects in each treatment. The incidence of SC injection site reactions will be summarized by treatment, time points post-injection, reaction, and severity (absent, mild, moderate, and severe). Injection site reaction will also be summarized by maximum severity and visit at 15 minutes, 30 minutes and 1 hour post injection. The proportion of the most extreme reactions among injections throughout all 5 visits will be calculated. In addition, the overall impact on daily living (severity and duration) of subject's injection site reactions will also be summarized by treatment. A listing will also be provided.

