11.6 Tolerability of Icatibant Therapy

TEAEs considered related to icatibant therapy will be summarized by treatment according to system organ class (SOC) and preferred terms (PT).

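### SAP 11.1 rules out all non-serious injection site reactions as AEs without limiting this to investigational product, which conflicts with the protocol's rule for icatibant reactions

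*SAP*

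**What the plan says.** Protocol 7.2.3.10 has two rules for injection site reactions.

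- **Investigational product.** The section opens with "Investigational product SC injection site reactions will be captured in the local tolerability CRF". The same paragraph adds: "Injection site reactions that do not meet the criteria of an SAE will not need to be reported as an AE".
- **Icatibant.** The section closes by saying that a reaction to icatibant given as rescue "will be reported as an AE with causality linked to icatibant". No seriousness condition is attached.

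Protocol 5.2.1 is consistent with the second rule: "Adverse events associated with medications used in the treatment of acute angioedema attacks will be captured on the AE CRF". Protocol 8.1.2 likewise allows an AE to be judged related to icatibant.

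SAP 11.1 has one rule: "In addition, angioedema attacks and ISRs will not be considered AEs unless they satisfy serious criteria according to the protocol". The sentence is repeated almost word for word later in the section. Neither occurrence says which injections it covers.

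SAP 11.6, on icatibant tolerability, is a single sentence: "TEAEs considered related to icatibant therapy will be summarized by treatment according to system organ class (SOC) and preferred terms (PT"). SAP 11.5 summarises injection site reactions separately and takes the worst of 15 assessments. SAP 16 declares no departure from the analyses in the protocol.

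**The concern.** The protocol's exemption from AE reporting belongs to investigational product, whose local reactions have their own CRF and their own summary. Icatibant reactions have neither, so the protocol sends them to the AE CRF. The SAP carries over the exemption but not its scope, and it does not carry over the icatibant rule at all.

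Safety and tolerability of icatibant is a stated secondary objective (Protocol 2.2.2, SAP 3.2), and SAP 11 lists tolerability of icatibant among the safety endpoints. Icatibant is injected subcutaneously in the abdomen (Protocol 5.2.1), so local reactions are a relevant part of its tolerability. The protocol gives them a sentence of their own, listed as a clarification under Amendment 3 in Appendix 6. A tolerability table without them would not report what the protocol set out to collect.

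**Working it through.** No sample size, error rate or event count enters here. The check follows one type of record through the two documents: a non-serious injection site reaction in an adult who injected icatibant for an attack.

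1. **Is it an AE under the protocol?** Yes. Protocol 7.2.3.10 makes it one, linked to icatibant, and Protocol 5.2.1 puts it on the AE CRF.
2. **Is it an AE under SAP 11.1 as worded?** No. It is an injection site reaction and it is not serious. The abbreviation ISR is expanded in the SAP only in the footnote to the schedule of assessments (Section 2.4), as injection site reaction, with no product named.
3. **Is it a TEAE?** SAP 11.1 defines a TEAE as an AE that meets timing or severity conditions. If the record is not an AE, it cannot be a TEAE. It therefore drops out of the TEAE summaries by system organ class, preferred term, severity and relationship.
4. **Is it in the SAP 11.6 table?** No. That table draws only on TEAEs related to icatibant, and nothing in 11.6 adds injection site reactions back.
5. **Is it in the SAP 11.5 summary?** No. The rule there is "Subjects will be counted in each category only once, the worst reaction among 15 assessments will be counted", and the section refers to 5 visits. Protocol Tables 1 and 2 give investigational product at the site at dosing visits 1, 8, 16, 24 and 28 of each period, and Protocol 7.2.3.10 sets three post-injection time points (15 minutes, 30 minutes, 1 hour). 5 visits × 3 time points = 15 assessments. The count is fully used up by investigational product injections.
6. **Is it in another summary?** None is specified. The diary asks for side effects of icatibant (Protocol 7.2.2.4), but SAP 11.6 defines no diary-based table.
7. **Is it in a listing?** Yes. SAP 11.1 lists all AE information held on the eCRF.

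As worded, then, the record is collected and listed but appears in no summary table. A serious icatibant reaction would stay in, since both documents treat it as an AE.

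**The case against.** The strongest reply is that ISR in this SAP simply means a reaction to investigational product. The ISR row of the schedule refers to investigational product injections, and SAP 11.5 carries the unqualified title Injection Site Reaction yet plainly covers only those. The protocol's own exemption sentence is equally unqualified and takes its scope from the paragraph around it; SAP 11.1 may just be a shortened copy. The SAP presents itself as an elaboration of protocol amendment 4 and declares no changes, so a reading that agrees with the protocol should be preferred. SAP 11.1 also gives no preferred-term list or flag for removing records from the AE data. The sentence could mean only that local tolerability records are not to be imported into the AE tables. The table specifications are in a separate document.

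Much of this stands. The narrower reading is plausible, and the omission is conditional on a programmer applying the sentence literally. What does not stand is that the text settles the matter. In the protocol, the surrounding paragraph limits the exemption and a separate sentence sets the icatibant rule; SAP 11.1 has neither. The reference to the protocol at the end of the SAP sentence attaches to the serious criteria, not to which injections are meant. SAP 16 shows that no change was declared, but it does not tell a programmer which of two conflicting rules to use. Two competent programmers could produce different 11.6 tables from the same data.

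**Conclusion.** The conflict between SAP 11.1 and Protocol 7.2.3.10 is real, and the passages must be reconciled. Read literally, the SAP rule removes every non-serious icatibant injection site reaction from the TEAE summaries and from the SAP 11.6 table; read as limited to investigational product, it removes none. The documents give no rate for these reactions, so their share of icatibant-related events is unknown and any percentage would be a guess.

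A reader might infer more than this, and the documents do not support it:

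- **That the reactions are lost altogether.** They are not. They remain on the AE CRF and in the AE listing.
- **That the omission is certain.** It depends on the literal reading of SAP 11.1, and the table specifications are not available to confirm either reading.
- **That the SAP deliberately overrides the protocol.** SAP 16 declares no change, and a shortened restatement that lost its scope is the simpler explanation.

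The effect is limited to descriptive safety tables for rescue medication. No hypothesis test, no primary or key secondary endpoint and no other efficacy analysis depends on it. It is still worth correcting, because the SAP states a rule that conflicts with the protocol on a secondary objective.

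**What to change.** In SAP 11.1, limit both sentences to injection site reactions to investigational product. Add one sentence saying that injection site reactions to icatibant, which Protocol 7.2.3.10 has reported as AEs, are included in the TEAE tables and in Section 11.6. Repeat that inclusion in SAP 11.6, and check that the separate table specifications (SAP 18) do not filter these records out.

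The cost is a phrase in two places and a sentence or two. The protocol already places the records on the AE CRF, so no new data are needed, and no clinical procedure changes.

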11.2 Clinical Laboratory Variables

Descriptive statistics for clinical laboratory values (in SI units) and changes from baseline at each assessment time point (baseline, 8a, 16a, 24a, 28a, 8b, 16b, 24b and 28b) will be presented by treatment for the following clinical laboratory variables:

Hematology: WBC count (total and differential), RBC count, hemoglobin, hematocrit, and platelet count.

Biochemistry: aspartate aminotransferase (AST), alanine aminotransferase (ALT), alkaline phosphatase (ALP), creatine phosphokinase (CPK), Blood urea nitrogen (BUN), creatinine, carbon dioxide (CO2), albumin, total protein, glucose, potassium, sodium, chloride, and phosphorus

Coagulation: Prothrombin time (PT), international normalized ratio (INR), activated partial thromboplastin time (aPTT) and D-dimer.

Urinalysis with microscopy: pH, Dipstick (protein, glucose, ketones, hemoglobin), Specific gravity, Microscopic evaluation (red blood cells, white blood cells, crystals, casts, bacteria).

Clinical laboratory test values are potentially clinical important (PCI) if they meet either the low or high PCI criteria listed in Table 6 and fall outside the laboratory's normal range in the same direction (high or low) as their PCI criteria. Subjects with post-dose PCI values will be summarized by treatment and also listed. In addition, The number of subjects with a nonmissing result, and the number and percentage of subjects with a clinically significant result less than the lower limit of normal, non-clinically significant result less than the lower limit of normal, within the normal range, non-clinically significant result more than the upper limit of normal, and clinically significant result more than the upper limit of normal will be summarized by visit and treatment.
			Criteria for Clinic Abnormalities ¹	ally Significant Laboratory
Parameter	Age Range	Gender	Low	High
Hematology	. 11		N T 4	
Eosinophils (%)	All	Male, Female	NA	>4 x ULN
Hematocrit	All	Male, Female	<0.6 x LLN	>1.3 x ULN
Hemoglobin	All	Male, Female	<0.6 x LLN	>1.3 x ULN
Neutrophils (%)	All	Male, Female	<0.5 x LLN	NA
Platelets	All	Male, Female	<0.4 x LLN	>2 x ULN
Leukocytes (WBC)	All	Male, Female	<0.5 x LLN	>2 x ULN
Coagulation				
Intl. Normalized Ratio (INR)	All	Male, Female	NA	>1.5 x ULN
Activated Partial Thromboplastin Time (aPTT)	All	Male, Female	NA	>2.0 x ULN
Chemistry				
Albumin	All	Male, Female	<0.6 x LLN	NA
Alkaline Phosphatase	All	Male, Female	NA	>3.0 x ULN
Alanine Aminotransferase (ALT)	All	Male, Female	NA	>3.0 x ULN
Aspartate Aminotransferase (AST)	All	Male, Female	NA	>3.0 x ULN
Blood Urea Nitrogen (BUN)	All	Male, Female	NA	>3.0 x ULN
Chloride	All	Male, Female	<0.8 x LLN	>1.2 x ULN
Creatinine	All	Male, Female	NA	>1.5 x ULN
Potassium	All	Male, Female	<0.85 x LLN	>1.2 x ULN

Table 6: Criteria for Potentially Clinically Important Laboratory Tests

			Criteria for Clinically Significant Laboratory Abnormalities ¹		
Parameter	Age Range	Gender	Low	High	
Glucose	All	Male, Female	<0.6 x LLN	>3.5 x ULN	
Sodium	All	Male, Female	<0.9 x LLN	>1.1 x ULN	

Table 6: Criteria for Potentially Clinically Important Laboratory Tests

NA=Not Applicable; LLN=Lower Limit of Normal; ULN=Upper Limit of Normal; Intl.=International.

If criteria in both directions are shown for a single parameter, then abnormalities in each direction are summarized separately.

11.3 Vital Signs

Descriptive statistics for vital signs (e.g. systolic and diastolic blood pressure and pulse) and their changes from baseline at each post-dose visit will be presented by treatment.

Vital sign values will be considered PCI if they meet the observed value criteria or the change from baseline criteria listed in Table 7. Subjects with post-baseline PCI values will be summarized by treatment and a supportive listing of subjects with post-baseline PCI values will also be provided. All vital signs results will be listed for the Safety Set.

Table 7:	Criteria f	or Potentially	Clinically	Important	Vital Signs
		/			

Vital Sign Paramatar	Flag	Criteria
	Flag	Observed Value
Systolic blood pressure (mmHg)	High	Increase of ≥ 20 from baseline value and ≥ 140
	Low	Decrease of ≥ 20 from baseline value and ≤ 90
Diastolic blood pressure (mmHg)	High	Increase of ≥ 15 from baseline value and ≥ 90
	Low	Decrease of ≥ 15 from baseline value and ≤ 50
Pulse rate (beats per minute)	High	Increase of > 15 from baseline value and ≥ 100

Vital Sign Paramotor	Flag	Criteria	
	riag	Observed Value	
	Low	Decrease of > 15 from baseline value and ≤ 45	
Temperature (°C)	High	> 38.3	
	Low	< 35	

Table 7: Criteria for Potentially Clinically Important Vital Signs

11.4 Electrocardiogram

All 12-lead ECG collected at the screening visit will be listed for the Safety Set.

11.5 Injection Site Reaction

A summary of SC injection site reactions will be summarized by treatment. The categories in this summary include: any injection site reaction, any severe reaction, any mild reaction, and any moderate reaction. Subjects will be counted in each category only once, the worst reaction among 15 assessments will be counted. The percentage will be calculated from the total number of subjects in each treatment. The incidence of SC injection site reactions will be summarized by treatment, time points post-injection, reaction, and severity (absent, mild, moderate, and severe). Injection site reaction will also be summarized by maximum severity and visit at 15 minutes, 30 minutes and 1 hour post injection. The proportion of the most extreme reactions among injections throughout all 5 visits will be calculated. In addition, the overall impact on daily living (severity and duration) of subject's injection site reactions will also be summarized by treatment. A listing will also be provided.

11.6 Tolerability of Icatibant Therapy

TEAEs considered related to icatibant therapy will be summarized by treatment according to system organ class (SOC) and preferred terms (PT).

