4.4 Safety Set

All subjects who have taken at least 1 dose of investigational product will be included in the safety set.

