9. PRIOR AND CONCOMITANT MEDICATION

Prior and concomitant medications will be coded using the World Health Organization-Drug Dictionary (WHODRUG) Version June 2017.

Prior medications are defined as medications with start time prior to the time of investigational product administration.

Concomitant medications are defined as medications with a start times after the time of investigational product administration or medications with a start time prior to investigational product administration but continuing after treatment, and with a start time before the 1-month post-treatment visit, inclusive.

Medical/surgical procedures performed during the treatment (between the dates of the first dose and the 1-month post-treatment visit, inclusive) will be recorded on the CRF, along with the date, time, and reason for the procedure.

Prior medication usage will be summarized using the number and percentage of subjects receiving each medication by treatment sequence, a total of crossover sequences and a total of all sequences, by indications, level 1 of the Anatomic Therapeutic Chemical (ATC) classification system and preferred term (PT) within the Safety Set and Full Analysis Set. Multiple medication usage by a subject in the same preferred term category will be counted only once. Concomitant medication/procedure by treatment, indications, ATC level 1, and preferred term (PT) within the Safety Set and Full Analysis Set. For this summary, concomitant medications will be assigned to a treatment if they are recorded at least once within the period corresponding to that treatment. Medical/surgical procedures will be listed for the Safety Set.

All non-study medications taken during the study will be listed and flagged with prior, concomitant and post treatment (taken after the 1-month post-treatment visit, exclusive) medications for Safety Set. Medical/surgical procedures performed during the treatment (between the dates of the first dose and the 1-month post-treatment visit, inclusive) will also be listed for the Safety Set.

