11. SAFETY ANALYSES

The safety analyses will be performed by treatment using the Safety Set. Safety endpoints include adverse events (AE), clinical laboratory assessments, vital signs, ECG findings, SC injection site reactions, C1 INH antibody status and patient-reported tolerability of icatibant therapy for acute angioedema attacks. The last assessment prior to the first dose of investigational product in treatment period 1 will be used as baseline for all safety analyses.

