17. DATA HANDLING CONVENTIONS

17.1 General Data Reporting Conventions

Continuous variables will be summarized using the following descriptive statistics: n, mean, SD, median, minimum, and maximum. Categorical and count variables will be summarized by the number of subjects (n) and the percent of subjects in each category.

Unless specified otherwise, min/max will be presented to the same decimal places as the raw data. Percentage, mean and median will be presented to 1 more decimal places than the raw data. Standard deviation and standard error will be presented to 2 more decimal places than the raw data.

In addition, *p*-values will generally be presented to 4 decimal places; values less than 0.0001 will be presented as <0.0001.

Treatment Columns Displayed in Summary Tables

The treatment columns displayed will differ between summary tables. Tables that summarize information only from the prior treatment or post-treatment periods will generally have the following treatment columns displayed:

Sequence A/B

Sequence B/A

Sequence A/A

Total

Tables that summarize efficacy and safety information only from the treatment period will generally have the following treatment columns displayed:

Treatment A: 2000 IU C1 INH

Treatment B: Placebo

Total (if needed)

Tables that summarize efficacy and safety information from the treatment period and treatment sequence will generally have the following treatment columns displayed:

Sequence A/B: Period 1: 2000 IU C1 INH

Sequence A/B: Period 2: Placebo

Sequence B/A: Period 1: Placebo

Sequence B/A: Period 2: 2000 IU C1 INH

Sequence A/A: Period 1: 2000 IU C1 INH

Sequence A/A: Period 2: 2000 IU C1 INH

Tables that summarize efficacy and safety information from the treatment period with different treatment sequence combinations will generally have the following treatment columns displayed:

Treatment A from Sequence A/B and B/A: 2000 IU C1 INH

Treatment A from Sequence A/A: 2000 IU C1 INH

Treatment A Overall: 2000 IU C1 INH

Treatment B: Placebo

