18. TABLE OF CONTENTS FOR TABLES, FIGURES, AND LISTINGS

The Mock TFLs will be provided in a separate document.

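### SAP 11.6 sets no icatibant-exposure restriction, so under the SAP's default format its table would mix icatibant tolerability with how often icatibant was used

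*SAP*

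**What the plan says.** SAP 11 opens with a general rule: "The safety analyses will be performed by treatment using the Safety Set". The endpoints it then lists include "C1 INH antibody status and patient-reported tolerability of icatibant therapy for acute angioedema attacks", so the rule covers icatibant. SAP 4.4 defines the population: "All subjects who have taken at least 1 dose of investigational product will be included in the safety set". Receipt of icatibant plays no part in that definition.

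SAP 11.6 is a single sentence: "TEAEs considered related to icatibant therapy will be summarized by treatment according to system organ class (SOC) and preferred terms (PT". It names no icatibant-treated subset, no denominator and no rate per injection or per attack. Protocol 9.9 says only that icatibant tolerability will be summarised.

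The SAP's general format for adverse events is in SAP 11.1: "The number and percentage of subjects reporting any TEAEs, and absolute count of events will also be summarized in the following ways". Table layouts are not in the SAP; section 18 says "The Mock TFLs will be provided in a separate document".

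Protocol 5.2.1 gives icatibant to adults whose attack, in the investigator's opinion, requires medical intervention. Adolescents receive local standard of care instead. Assessing the safety and tolerability of icatibant in adults is a listed secondary objective (Protocol 2.2.2, SAP 3.2).

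**The concern.** The population stated for this table does not match the drug it describes. The Safety Set suits investigational-product reactions, because everyone in it was injected with investigational product. For icatibant it also contains adolescents and adults who never had an icatibant-treated attack.

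Under the default format this has two consequences.

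- **Dilution.** Subjects never given icatibant sit in the denominator, so the percentage understates the frequency of related events among users.
- **Dependence on use.** A subject with more injections has more opportunities for a related event, if risk accrues per injection. Percentages and event counts then follow icatibant use, and use follows attack rate. The sample size section (Protocol 9.6, SAP 2.5) plans for a difference of 1.0 attack per month between active and placebo, so unequal use is to be expected if the drug works as hoped.

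At stake is one stated secondary objective. Protocol 7.2.3.10 has icatibant injection site reactions reported as adverse events linked to icatibant, so the table should have events in it. A reader could take a column difference caused by rescue use for a difference in how icatibant is tolerated.

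**Working it through.** The documents give no figure for this point, so there is none to reproduce. The steps below show the mechanism and then an illustration.

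**Identity.** Safety Set percentage = (share of subjects using icatibant) × (percentage with a related event among users). The understatement relative to users is therefore 1 − share.

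**Inputs from the documents.** Each period lasts 98 days and a month is 30.4 days, so T = 98/30.4 = 3.224 months. The A/B and B/A sequences have 26 + 26 = 52 subjects, each contributing one active and one placebo period. SAP 17.1 has a layout that keeps these apart from A/A: "Treatment A from Sequence A/B and B/A: 2000 IU C1 INH".

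**Assumed inputs.** Attack rates of 1 per month on active and 2 on placebo; 40% of attacks treated with icatibant; a 20% risk of a related event at each treated attack on both treatments; Poisson attacks.

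**Formulas.** Mean treated attacks m = rate × T × 0.40. Share using = 1 − exp(−m). Any related event = 1 − exp(−0.20m). Among users = any event / share. Treated attacks per user = m / share.

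| | Active | Placebo | Gap |
|---|---|---|---|
| m | 1.289 | 2.579 | |
| Share using | 72.5% | 92.4% | |
| Safety Set percentage | 22.7% | 40.3% | 17.6 points |
| Users only | 31.4% | 43.6% | 12.2 points |
| Treated attacks per user | 1.78 | 2.79 | |
| Per treated attack | 20% | 20% | 0 |

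With a 5% risk per treated attack, the Safety Set shows 6.2% against 12.1%, and users only 8.6% against 13.1%.

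**How much a user-only denominator removes.** In the table, 12.2/17.6, about 70% of the gap, remains after restriction to users. That share depends on the model. With the same rates and risk it is about 56% if 20% of attacks are treated and about 48% if 10% are. If risk is instead fixed per user, restriction removes the whole gap: with a 30% risk in users and use of 40% against 80%, the Safety Set shows 0.40 × 30% = 12% against 0.80 × 30% = 24%, and users only shows 30% on both.

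**Range of the understatement (1 − share).**

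- Active: 0.6% (2 attacks per month, 80% treated) to 64% (0.35 per month, 40% treated).
- Placebo: 2% to 8% (3 down to 2 attacks per month, 40% treated).
- If 0% to 10% of subjects are adolescents who never receive icatibant (assumed), the main illustration gives 28% to 35% on active and 8% to 17% on placebo.

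**Pooling A/A into the active column.** The 14 A/A subjects contribute two active periods each. Share using = (52 × 0.7246 + 14 × 0.9241)/66 = 76.7%. The Safety Set percentage is 26.5%, and 34.5% among users. The gap to placebo is 13.8 points, or 9.1 points among users.

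**The case against.** Four arguments can be made for the plan as it stands.

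1. **Section 11.6 promises no percentage.** It states a summary by treatment, SOC and PT. SAP 11.5, just above it, expressly takes its percentage from all subjects in each treatment; 11.6 has no such sentence. The shells are a separate document and could use icatibant users as the denominator. This stands. A reader might infer that the SAP prescribes a Safety Set percentage for icatibant events, but it does not. The concern is conditional on the default format being followed. The stated population is still the Safety Set, and nothing in either document narrows it for 11.6.

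2. **Other outputs supply the denominators.** SAP 9 summarises concomitant medication by treatment in the Safety Set, where "concomitant medications will be assigned to a treatment if they are recorded at least once within the period corresponding to that treatment", so users per treatment can be found. SAP 10.4 summarises attacks by acute therapy and treatment, though in the Full Analysis Set. This stands in part: a reader could approximate the right rates by combining tables, but none is linked to 11.6. The injection-count summary in SAP 10.4 stops at the first three attacks of a period. At the illustrated rates that covers about 46% of placebo and 75% of active attacks, or 83% and 96% if it means the first three icatibant-treated attacks.

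3. **The default format also gives event counts.** Counts are free of the never-user denominator, but without the number of injections or treated attacks beside them they still rise with use.

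4. **No comparison between columns is planned.** This stands. A reader might infer that the plan intends to contrast icatibant tolerability on active with that on placebo; neither document proposes such a test. The by-treatment layout still places the two figures side by side.

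**Conclusion.** The point holds as a minor one. SAP 11 puts icatibant tolerability in a population defined by a different drug, and 11.6 does not correct this. With the default adverse-event format, the percentages would include subjects never given icatibant, and percentages and counts would follow rescue use. The table would then understate tolerability problems among users and could show a column difference with none in tolerability.

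The size cannot be derived from the documents. Attack rates by treatment, the fraction treated with icatibant, the event risk and the adolescent share are all assumed, and the resulting understatement on active runs from negligible (0.6%) to large (64%). A reader might also infer from the main illustration that a user-only denominator always leaves most of the imbalance. That holds only if risk accrues at each treated attack, and even then the share left depends on how many attacks are treated.

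**What to change.** In SAP 11.6:

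1. Base the table on Safety Set subjects with at least one icatibant injection, counted within the relevant treatment period for by-treatment columns.
2. Make the pooled total the main display. SAP 17.1 already allows a total column where needed.
3. Show the number of users and of injections in each column header.
4. Give icatibant-related events per injection or per icatibant-treated attack, because a user-only percentage may still differ through repeat use if risk accrues per injection.

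The cost is a few lines of SAP text and one descriptive table. No new data are needed: Protocol 5.2.1 has the dose and time of attack medications recorded in the CRF, and Protocol 7.2.2.4 has subjects record icatibant injection times in the diary.
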